Study Protocol and Statistical Analysis Plan

Does the Improved Coordination of Care for Fall- and Fracture Prevention in Oslo Have Effect on the Rate of Hip Fractures, Need of Nursing Homes or Death?

RCN296587

January 2. 2023

The study is an evaluation of a new patient follow-up for fall- and fracture prevention in the municipality of Oslo with improvement of coordination of care for elderly (65 years or older, 65+) at risk of fall injuries.

The two major innovations in this initiative are 1) the systematic approach to improving care coordination within the health care system as well as 2) including osteoporosis evaluation in the fall risk assessment in order to reduce risk of fall related fractures.

In this study, the two city boroughs of Nordstrand and Østensjø, who initiated the intervention, are compared with a control group consisting of the other 13 city boroughs of Oslo in a controlled before and after study design.

The care coordination implemented is in line of the framework Øvretveit used in his summary review "Does clinical coordination improve quality and save money?" (2011)ⁱ, and which WHO later adopted in their practice brief "Continuity and coordination of care" (2018)ⁱⁱ. The major steps in the intervention in Oslo are as follows:

- Needs assessment and user involvement. The intervention started with the chief medical officers in the areas of intervention realizing the health burden of hip fractures within their boroughs, as well as the lack of care coordination in the delivery of preventive measures. The steps of the intervention were developed as a cooperative effort with the local health professionals who delivered the services, the chief medical officers in the boroughs and specialists in geriatrics, osteoporosis and injuries at Oslo University Hospital.
- Case finding of individuals with increased risk of a fall injury. In the start of the intervention this was primarily done within the boroughs through physiotherapists and occupational therapists who looked for patients with increased risk of falling in their clinical practices. Education on fall risks and possible follow-up was also given to the General Practitioners (GPs) and at the community centers for case finding. From September 2017 the Injury Clinic at Oslo University Hospital started sending so-called "fall reports" to the boroughs when 65+ patients with fall related injuries had been treated at the clinic, assisting the boroughs in identifying cases and targeting this high-risk population in their preventive initiatives.
- Shared, collaborative single point of entry to care in the boroughs. This is the address to where the fall reports from the Injury Clinic were sent. The same address was conveyed to the GPs and the other health professionals to send messages whenever a need for falls risk assessment and intervention was detected. On the receiving end of this address, is a care coordinator with extensive knowledge about the local health care system and the fall prevention pathway who forwards the messages to launch the right follow-up.
- A cross-sectoral plan for follow-up with role clarification. This was a major part of improving the coordination of care. Who identifies the elderly at risk of fall injuries and how (case finding)? Who performs the fall risk assessments? What measures are taken to reduce risk, who delivers these interventions and how are the at-risk-patients recruited into the follow-up? Both the leadership and those who delivered the services within the boroughs were included in the planning process. The cross-sectoral plans were developed both separately within the two boroughs and some parts in coordination with the Injury

Clinic, specialists at the University Hospital and the Department of Public Health of the Municipality of Oslo.

- Interdisciplinary teams were established in the two boroughs, consisting of those who did fall risk assessments through home visits. The teams consisted mainly of physiotherapists and occupational therapists. Nurses, nutritionists, and clinical pharmacologist were added later. These teams received referrals for risk assessments from the single point of entry, sent from the Injury Clinic as fall reports and as well messages from by other health professionals within the boroughs.
- Tools for multifactorial falls and fracture risk assessment, leading to tailored interventions
 were developed as instruments to ensure the quality of care. The content of these
 assessment tools was based on best-practice and evidence-based, but the format was
 adapted by local health professionals to fit their practices and workflow.
 - The first assessment tool developed, was an interdisciplinary assessment checklist for home visits. The main areas that were assessed was gait and need for physiotherapy and exercise, safety in home environment, need of medical examination, sight, footwear, nutrition status, and support network. This assessment tool has been revised and improved several times in accordance with developing evidence and user preferences.
 - The second tool developed was a checklist for the GPs consisting of a list of medical conditions to consider in patients who had fallen, suggested blood work, guidelines for osteoporosis evaluation, tools for medication review and a description of referral pathways.
 - 3. The third assessment tool developed, was for the doctors at the Injury Clinic to help them to evaluate whom of the fall injury patients to refer for further follow up in the boroughs and/or the geriatric department for falls risk assessment and/or osteoporosis evaluation. A secretary assisted in the logistics of sending the fall reports to the single point of entry in the boroughs.
 - 4. FRAX, an established fracture risk assessment tool, was introduced to all health professionals, but to the GPs in particular.
- Information sharing. Standardized messaging was introduced from the actors responsible for the case finding to those who did falls risk assessment and further to those who performed risk-reducing measures. For instance, the fall reports from the Injury Clinic were a specified type of message with a planned follow-up. Involving the GP in the information loop was key to improve coordination.
- Primary and specialist care referral pathways and processes. The referral pathway to the
 geriatric departments was strengthened with the aim of both increasing the number of
 referrals and for the referrals to be more appropriate, with focus on patients with multi
 morbidity, polypharmacy, and suspected syncopes. Furthermore, access to osteoporosis
 evaluation and intravenous treatment of osteoporosis with zoledronic acid was improved.
- Champions in the two boroughs, at the Injury Clinic and in the Public Health Department of Oslo were chosen, aiming to create enthusiasm and carry the intervention forward within their organizations. The champions in the boroughs worked in close coordination

with the two Chief medical officers of the boroughs. The intervention received yearly grants ("Samhandlingsmidler") from a joint committee from the Specialist and Primary health care in Oslo for improving coordination of care from August 2016, which made it possible to allocate time for working on this project. The yearly grants amounted to 0,3 – 1 yearly salary mainly distributed between the champions, so most of the intervention used resources within the normal budget and activity. The champions mobilized colleagues and experts, developed the assessment tools, educated of health professionals and were a driving force in expanding the intervention.

- Tailored interventions to reduce risk of falls and fractures. The two intervention boroughs already offered, as all other boroughs in Oslo, strength and balance exercise groups and had occupational therapists who did home safety assessments on referral before study start. The new care coordination led to a mapping of the existing variety of exercise groups, and some increase both in the number and variety of the exercise options. Other interventions like safety measures at home, different aids, nutrition, osteoporosis treatment, medication assessment and geriatric evaluation was also better described and made available. The extensive mapping of the local intervention possibilities was useful and was utilized as a menu to choose from when tailoring interventions for the individual after a multi factorial risk assessment.
- Collaborative training and education were offered for all health care professionals involved in the fall prevention pathways; all those involved in case finding, coordination, risk assessments and preventative interventions. The champions were responsible for organizing the education. This was offered in a smaller scale within local health centers and clinics, gatherings for all the GPs within the two boroughs, and from august 2018 through bigger events arranged annually by the Public Health Department in Oslo. The education focused on what may increase the risk of falling, osteoporosis, effect of different interventions, and sharing of practices and experiences.
- The main technology enabler in this intervention, was the digitalization in 2018 of the home visit assessment tool in the Electronic Patient Records (EPR) for the boroughs. In addition, a way of registering falls in the same EPR as well as a clear routine for how to document the multifactorial assessment and the follow up within this system, was a great support for those who did the home assessments and follow-up interventions. Digitalization of the fall reports in 2018 from the Injury Clinic, also was an improvement.

Timeline

Improving care coordination is a process. The investigators have, however, chosen to define these dates as the start of intervention, as this was the time when the systematic needs assessment together with the interdisciplinary and cross-sectoral approach to the fall-risk-prevention-problem, started.

These were the milestones which were chosen as start dates of the intervention:

1. Start of intervention in Nordstrand borough is set to January 1, 2015.

The Chief Medical Officer in Nordstrand mobilized the health professionals in a systematic needs assessment. They improved case finding, developed a checklist for multifactorial falls risk assessment through home visits, recruited more elderly at risk into exercise programs, and started education of health professionals including the GPs in coordination with the geriatricians at the University Hospital and local nursing homes. They also improved primary prevention with winter road safety measures and education of the general elderly population on fall risks and safety measures.

After Østensjø and the Injury Clinic at Oslo University Hospital joined the intervention in September 2016, the intervention in Nordstrand was done in collaboration and coordinated with these partners.

2. Start of intervention in Østensjø borough is set to September 1, 2016.

Østensjø started a collaboration with Nordstrand borough and the Injury Clinic in September 2016 after a grant proposal ("Samhandlingsmidler") was awarded funding. This led to a development of a formal multifactorial falls and fracture risk assessment tool for GPs, a revision of the interdisciplinary falls risk assessment tool from Nordstrand for home visits, establishing referral pathways within primary care and with specialist care established. In addition, education programs for both GPs and other health professionals in primary care was strengthened. Local champions were chosen and interdisciplinary working groups were established.

3. The Injury Clinic supported case finding from September 2017

All municipalities started receiving **fall reports** regarding consenting patients with fall injuries treated at the Injury Clinic at the University Hospital in Oslo from September 2017. This improved the case finding in both Nordstrand and Østensjø, who already had a coordinated care plan in place, which were presumed to be the crucial part of the intervention. The 13 other municipalities did not have the same coordinated care. Their patients received care as usual, which varied between the boroughs.

4. The end of the study period is set to December 31. 2019

The intervention in Oslo expanded to include most of the city boroughs after 2019. From January 2020 five more boroughs started care coordination, another five during 2021 and further one in 2022. The end of the study period with comparison between the two boroughs who started this intervention and the others, is therefore set to the end of 2019, before the 13 others began their systematic coordination of care.

Statistical Analysis Plan

The investigators will use a controlled before and after study design to evaluate this intervention.

The cohort

All elderly 65 age or older in Oslo are included in Oslo Fall Cohort with registry data from Statistics Norway, the National Population Registry, Norwegian Patient Registry (NPR), and the Electronic Patient Records for the health services in the local municipalities. Data is available on all participants from 2010 and the investigators will start following them from January 2012 until December 2019 with the intervention starting as specified in the timeline (see above). The study will follow each cohort participants prospectively and analyze the data by Cox proportional hazards regression or similar.

Fall injury will be included as a time-varying exposure variable. The individuals in the cohort are all registered as non-fallers until they are registered with a new fall injury in the NPR database, when they shift status to fallers.

Exposure categories

• Fallers in the intervention boroughs

Fallers 65+ years from the borough of Nordstrand from January 1. 2015 Fallers 65+ years from the borough of Østensjø from September 1. 2016

• Fallers in the control boroughs

Fallers 65+ years from all the 13 other boroughs of Oslo.

Non-fallers

All non-fallers from the complete Oslo population 65+ years.

Main analysis: In the main analysis (2015-2019), fallers from the two intervention boroughs, Nordstrand (from January 2015) and Østensjø (from September 2016), will be compared with fallers from the control boroughs during the intervention. In addition, the two categories of fallers will also be compared with the non-fallers. A similar analysis will be performed before the intervention started using data from 2012-2013. Any differences between the intervention and control boroughs before the intervention started will be taken into account.

In a secondary analysis, the total incidence (not restricted to fallers) of hip fracture in the intervention boroughs will be compared with the incidence of hip fracture in the control boroughs, and a similar comparison will be made before the intervention started. Adjustment for possible time trends will be considered.

Primary outcome variables

- Hip fracture
- Admittance to nursing home, long term
- Death (all-cause mortality)

Secondary outcome variables

Other fall injuries

In each analysis, participants with a hip fracture or living in a nursing home at baseline will be excluded.

Statistical power

According to statistics from NPR before the intervention started, around 22% of the home dwelling elderly treated for a fall injury came from the intervention boroughs of Nordstrand and Østensjø.

If 22% of the patients with falls are exposed to the fall prevention intervention and 607 of all fallers suffer a hip fracture during a follow-up of five years (2015-2019), it will enable us to detect a relative risk reduction of 24% (RR= 0.76) at the 0.05 significance level with a power of 80%.

Data management and analysis

The Cohort Data is stored at Services for Sensitive Data (TSD) at the University of Oslo.

The analysis in the evaluation is based on registry data and no analysis relating the intervention to the outcomes has been done before registration in clinicaltrials.gov. The outcome variables are the same as indicated in the study protocol in the grant application to the Norwegian Research Council (NRC) in 2018.

¹ https://www.health.org.uk/publications/does-clinical-coordination-improve-quality-and-save-money

[&]quot; http://apps.who.int/iris/bitstream/handle/10665/274628/9789241514033-eng.pdf?ua=1

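### People with recent earlier fall injuries start in the non-faller reference, and the plan does not say whether fall status is reset or carried over on 1 January 2015

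*Combined protocol and SAP*

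**What the plan says.** All references are to the Statistical Analysis Plan part of the combined document.

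- **The cohort, data and follow-up:** "Data is available on all participants from 2010 and the investigators will start following them from January 2012 until December 2019". NPR is among the named sources.
- **The cohort, exposure:** "Fall injury will be included as a time-varying exposure variable". The starting state and the switch are then defined: "The individuals in the cohort are all registered as non-fallers until they are registered with a new fall injury in the NPR database".
- **Exposure categories:** the reference is one common pool, "All non-fallers from the complete Oslo population 65+ years".
- **Main analysis:** the first contrast, over 2015-2019, is intervention-borough fallers against control-borough fallers. The reference pool has a further role: "In addition, the two categories of fallers will also be compared with the non-fallers". The benchmark is defined by "A similar analysis will be performed before the intervention started using data from 2012-2013".
- **Exclusions, after the outcome lists:** "In each analysis, participants with a hip fracture or living in a nursing home at baseline will be excluded". An earlier fall injury is not among them.

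Nothing in the plan uses 2010-2011 to classify or remove earlier fallers. It does not define what makes a fall injury new. It does not say what happens on 1 January 2015 to someone injured in 2012-2014.

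**The concern.** There are two linked issues.

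First, a person with an NPR fall injury in 2011 and none since enters January 2012 as a non-faller. If such people keep a raised risk of hip fracture, nursing home admission or death, the reference hazard is too high and the planned faller-versus-non-faller HRs are too close to 1. The data needed to avoid this appear to be held already.

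Second, the 2012-2013 analysis is meant to be similar to the main one. Whether it is depends on an unstated choice. If status runs on continuously from January 2012, the main analysis begins with a stock of people injured up to three years earlier, while the before analysis begins with an empty faller group. The faller groups then differ between periods in time since fall, and the main-analysis reference has been cleared of 2012-2014 fallers while the before-analysis reference has been cleared of none. Left open, the choice could be made after results are seen.

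**Working it through.** **1. The plan's own figure.** The power statement is not in dispute but uses the same faller definition. Inputs from Statistical power: 22% exposed, RR 0.76, alpha 0.05 (two-sided assumed), power 80%.

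Events = (1.960 + 0.842)² / [0.22 × 0.78 × (ln 0.76)²] = 7.849 / (0.1716 × 0.0753) ≈ 607.3, or 608 rounded up, against 607 stated. It reproduces.

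**2. Share of the reference with a recent earlier injury.** The documents give no injury rate, so a yearly rate i of 2-5% is assumed. Over the two years 2010-2011, p = 1 − (1 − i)²:

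- i = 0.02: p = 1 − 0.98² = 0.040
- i = 0.05: p = 1 − 0.95² = 0.098

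**3. Dilution of the faller-versus-non-faller HR.** Let H be the true HR of fallers against people with no earlier injury, and r the HR of earlier fallers against the same group. Then observed HR = H / (1 − p + p·r). H and r are assumed.

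| H | r | p = 0.040 | p = 0.098 |
|---|---|---|---|
| 2 | 1.5 | 1.96 | 1.91 |
| 2 | 2 | 1.92 | 1.82 |
| 3 | 1.5 | 2.94 | 2.86 |
| 3 | 3 | 2.78 | 2.51 |

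For H = 2 the range is 1.96-1.82. For H = 3, with earlier fallers at full risk, it is about 2.8-2.5.

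**4. Intervention against control fallers.** Both faller groups are set against the same pool, so the divisor d = 1 − p + p·r is common. With a true ratio of 0.76, (0.76·H/d) / (H/d) = 0.76 for every d. The contamination cancels. The secondary analysis of total hip fracture incidence is not restricted to fallers and is untouched.

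**5. Status on 1 January 2015, the two readings side by side.**

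| | Start of before analysis (January 2012) | Start of main analysis (January 2015) |
|---|---|---|
| Reset | no fallers; everyone starts as a non-faller | no fallers; everyone starts as a non-faller |
| Carry-over | no fallers | fallers from up to three years (2012-2014) already in the faller groups |

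Under carry-over, with the same assumed rates, 1 − 0.98³ = 0.059 to 1 − 0.95³ = 0.143, so about 6-14% of the cohort would enter 2015 already as fallers (ignoring deaths and moves). None would in January 2012.

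**6. Link to the event count.** The plan does not say which faller definition lies behind 607. If the definition finally used gave 10-20% fewer events (an arbitrary illustration), 546 or 486 events would give 76% or 71% power for RR 0.76.

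**The case against.** The best case for leaving the plan alone is that its effect estimate does not depend on the reference. The leading contrast is faller against faller, the non-faller comparison is additional, and the before-period adjustment concerns differences between intervention and control boroughs. This stands, and it keeps the point minor.

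It can also be said that the exclusion rule speaks of a baseline in each analysis, which suggests separate starts and hence a reset, and that the word new hints at a wash-out. Both are hints. Neither settles how fall status is set.

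The illustration is fairly criticised as generous. For a given injury rate, repeat fallers, deaths among earlier fallers and the exclusion of people with a hip fracture or in a nursing home would all lower p. A risk that fades with time would lower r. The H = 3, r = 3 row is therefore an upper-end case.

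A reader might go further and infer that a reset itself creates a false change over time: two registered years of earlier falls (2010-2011) are ignored in 2012 but five (2010-2014) in 2015, so an HR of 3 would appear as 2.78-2.51 before and 2.52-2.07 in the main analysis. The documents do not support this. The two and the five reflect only where the data begin. Falls in 2007-2009 also sit, unseen, in the 2012 reference. At a stable rate the five years before either baseline give the same 10-23% share and the same dilution.

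The same reasoning answers the objection that a 24-month look-back leaves 2010-2012 fallers in the main reference but no registered ones in the before reference. At a stable rate, falls more than two years old remain in both alike.

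**Conclusion.** The concern holds in a limited form. As written, people with recent earlier fall injuries enter the non-faller reference and dilute the planned faller-versus-non-faller HRs. Under the assumptions shown, the loss is modest: from 2 to about 1.96-1.82, or from 3 to about 2.8-2.5. This rests on reading the statement about data from 2010 as covering NPR fall injuries, and on rates and HRs that the documents do not supply.

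That the two periods differ is a possibility and is not established. It arises under carry-over. Under a reset the rule is the same in both analyses and no artefactual change over time is shown. Nor does reference contamination bias the intervention-versus-control faller contrast. The reset or carry-over choice still matters for that contrast in another way, because it decides who is in the faller groups, how long ago they fell and how many events are counted.

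This is a worthwhile clarification and does not threaten the main comparison.

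**What to change.** Add to the plan:

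1. The same 24-month look-back in both analyses: 2010-2011 for the before analysis and 2013-2014 for the main analysis.
2. A definition of a new fall injury as the first one after the baseline of that analysis.
3. A separate prior-faller category for people with an injury in the look-back (or their exclusion from the reference) until a new injury occurs.
4. A statement that status is re-set by this rule on 1 January 2015.
5. A note on which faller definition gave the 607 hip fractures, with a recount if it differs from this one.

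The cost is a few sentences and one derived variable, from data that the plan says it holds. The reference group becomes slightly smaller. If 607 was counted with carried-over fallers, the event count for the faller contrast will be lower than stated, and the power statement should be updated.

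### The programme may change who becomes a registered faller in its two boroughs, so the faller-versus-faller comparison can be biased in either direction, and the 2012-2013 comparison cannot remove this

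*Combined protocol and SAP*

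**What the plan says.** Under The cohort, fall injury is a time-varying exposure: members are "registered as non-fallers until they are registered with a new fall injury in the NPR database, when they shift status to fallers". No diagnosis codes, severity threshold or type of contact are given. Exposure categories then counts intervention fallers from January 2015 in Nordstrand and from September 2016 in Østensjø. Main analysis compares them with fallers from the other 13 boroughs over 2015-2019, repeats the comparison on 2012-2013 data, and says that differences present before the start will be allowed for, without saying how.

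The programme description lists activities that could affect who reaches that registry entry:

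- Case finding bullet: "Education on fall risks and possible follow-up was also given to the General Practitioners (GPs) and at the community centers for case finding".
- Tools bullet: the GP checklist for patients who have fallen contains "tools for medication review and a description of referral pathways".
- Referral pathways bullet: the route to the "geriatric departments was strengthened with the aim of both increasing the number of" referrals and making them more appropriate, with a focus on multi-"morbidity, polypharmacy, and suspected syncopes".
- Timeline, item 1 (Nordstrand): "They improved case finding, developed a checklist for multifactorial falls risk assessment through home visits". The same item lists winter road safety and education of the general elderly population.
- Timeline, item 2 (Østensjø): "establishing referral pathways within primary care and with specialist care established".

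Timeline, item 3 says that the other 13 boroughs lacked the same coordinated care. The one analysis not restricted to fallers is secondary and covers hip fracture only.

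**The concern.** The comparison is conditional on an event that occurs after the programme has begun and that the programme may influence. If education or referral brings people into NPR who would otherwise not have been recorded, the intervention faller group differs in composition from the control faller group. The outcome rate per faller then moves even if nobody's risk has changed. Prevention can do the same by removing some falls: if mild falls are prevented, the remaining fallers are on average at higher risk, and a useful programme looks worse.

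The before-period comparison does not help, because the change in composition starts with the programme. All three primary outcomes are exposed. For hip fracture, the secondary total-incidence analysis offers a check. For long-term nursing home admission and death there is none. The plan lists other fall injuries as a secondary outcome, but nothing in it examines whether the rate or case-mix of newly registered fallers changed differently between borough groups.

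**Working it through.** **1. The plan's own figure.** Inputs from Statistical power: 22% of fallers exposed, 607 hip fractures, RR 0.76, significance level 0.05, power 80%. Schoenfeld's formula with a two-sided level:

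events = (1.960 + 0.842)² / [0.22 × 0.78 × (ln 0.76)²] = 7.849 / (0.1716 × 0.0753) ≈ 607.3, so 608.

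Power with 607 events is 79.98%. The figure reproduces and is not in dispute. It does assume that the two faller groups are comparable.

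**2. Why the before period does not correct the problem.** Let s be a stable ratio between borough groups and B the distortion from a changed faller mix. With no true effect, the before ratio is s and the after ratio is s × B. Dividing one by the other leaves B, so the distortion passes through in full.

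**3. Size under assumptions.** The documents give neither the extra registration nor the risk of those added. Let x be extra fallers as a fraction of those otherwise registered in the intervention boroughs, and r their outcome risk relative to the others. With no true effect:

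spurious RR = (1 + x·r) / (1 + x)

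| x | r = 0.25 | r = 0.5 | r = 1.5 |
|---|---|---|---|
| 5% | 1.0125/1.05 = 0.964 | 1.025/1.05 = 0.976 | 1.075/1.05 = 1.024 |
| 10% | 1.025/1.10 = 0.932 | 1.05/1.10 = 0.955 | 1.15/1.10 = 1.045 |
| 20% | 1.05/1.20 = 0.875 | 1.10/1.20 = 0.917 | 1.30/1.20 = 1.083 |

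Removal works in reverse. If prevention removes a fraction y of fallers with relative risk r, RR = (1 − y·r)/(1 − y). With y = 10% and r = 0.5 this is 0.95/0.90 = 1.056.

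**4. Chance of a significant result for hip fracture with no true effect.** The exposed share becomes a = 0.22(1 + x)/[0.22(1 + x) + 0.78], and events become d = 607 × [0.22(1 + x·r) + 0.78]. The test statistic is then centred at √(d·a·(1 − a)) × |ln RR|. For x = 20% and r = 0.5: a = 0.264/1.044 = 0.253, d = 607 × 1.022 = 620, centre = 0.94, rejection probability about 0.16. For x = 20% it is about 0.30 at r = 0.25 and about 0.14 at r = 1.5 (towards apparent harm). The nominal level is 0.05.

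**5. What would mimic the full design effect.** Solving for RR = 0.76 gives x = 0.24/(0.76 − r): 0.24/0.51 = 47% at r = 0.25 and 0.24/0.26 = 92% at r = 0.5.

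**The case against.** The strongest reply is that the link from programme to registry entry is not documented. Exposure is a fall injury in NPR. GP and community case finding feeds the boroughs' single point of entry, and the falls that the programme records go into the boroughs' own patient record system. Geriatric and osteoporosis referrals are not described as injury treatment, and the power section speaks of people treated for a fall injury. The Injury Clinic's fall reports follow an injury contact and went to all boroughs from September 2017, so they are not the source. This stands: that a referral creates a new fall-injury record is an inference, which the missing definition leaves open. Changed care-seeking after public education, and falls avoided through prevention, need no such link.

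A reader might infer that the added cases would be milder and that the bias therefore favours the programme. The documents do not support that. The referral pathway targets multi-"morbidity, polypharmacy, and suspected syncopes", which points to frailer patients, and prevention could remove mild falls.

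A reader might also infer that every one of these steps was confined to the two boroughs. That is not established. The referral and osteoporosis bullet names no borough, FRAX was introduced to health professionals generally, and the larger training events from August 2018 were run by the city's public health department. The plan says only that the others lacked the same coordination.

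Finally, the magnitude is assumed throughout, and small amounts of extra registration do little. That is also correct.

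**Conclusion.** The concern holds as a risk of bias of unknown sign and size. Group entry in the main period follows programme start, the programme may change it in the intervention boroughs, and nothing planned would detect or correct this for nursing home admission or death. Over the assumed range of 5% to 20% extra fallers, the spurious RR is about 0.88 to 0.98 at a quarter to half of the usual risk, and about 1.02 to 1.08 at 1.5 times the risk. At 20% and lower risk, the apparent reduction of 8% to 12.5% is about a third to a half of the 24% that the study is sized to detect. At 5% it is 2% to 4%. This mechanism alone would need 47% to 92% extra fallers to produce RR 0.76 at those risks.

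These values assume no true effect, constant relative risk among those added, and unchanged registration in the control boroughs. The plan should be changed, but the documents do not show that the main result will be wrong, or in which direction.

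**What to change.** Amend The cohort and the main and secondary analysis paragraphs of the SAP as follows.

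1. Tabulate newly registered fallers per 1,000 residents and their case-mix (acute contact, fracture, admission) by borough group for 2012-2013 and 2015-2019. This tests the concern directly, whichever way it runs.
2. Pre-specify a sensitivity analysis of all three primary outcomes in which faller entry is limited to acute injury contacts and planned outpatient contacts are left out. State the NPR codes and contact types used. Note that a further restriction to fracture or admission may itself be affected, because the programme aims to prevent fractures.
3. Extend the analysis not restricted to fallers, with its before-period comparison, from hip fracture to long-term nursing home admission and death. Interpret the main result alongside it.

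No rule is needed that makes a claim of benefit depend on the smaller restricted group. Such a rule would lack a clear criterion and would rest on fewer events than a full group with only 80% power.

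The cost is SAP text and extra runs on registry data, assuming that contact type and diagnosis are in the extract. The restricted group will give a wider interval, and the all-resident analysis a diluted effect, since most residents are not fallers exposed to the follow-up.
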